1.2 SCHEMA

1.3 SCHEDULE OF ACTIVITIES (SOA)

Procedures	Baseline / Screening	Day 1 of Week 1	8-Week Intervention									Post Intervention
	0	1	1	2	3	4	5	6	7	8	9	
Week	0	1	1	2	3	4	5	6	7	8	9	12
Prospective patients identified (Cohort Builder or Provider)	X											
Informed consent in person or over phone	X											
Verify eligibility in chart review or from [name]:	X											
• Medical history												
• Demographics												
Randomization	X											
Baseline Questionnaires (Listed below with)	X											
Shipment of VR device and/or study documents	X											
Technical onboarding call		X										
Milligram Morphine Equivalent (MME) Daily Dose	X										X	
Return of VR Device												X
Deliver honorarium						X					X	X
Self-Reported Questionnaires												
NIH developed baseline demographics, biological sex	X (Day 1)											
Daily Pain Medications Used	X										X	
Daily Pain Intensity	X										X	
Pain Catastrophizing Scale	X (Day 4)		X	X	X	X	X	X	X	X	X	
PROMIS Anxiety Scale	X (Day 4)		X	X	X	X	X	X	X	X	X	
PROMIS Pain Interference Scale	X (Day 4)		X	X	X	X	X	X	X	X	X	
The Pain Self-Efficacy Questionnaire (PSEQ) 2-item short form	X (Day 4)		X	X	X	X	X	X	X	X	X	
Simulator Sickness Questionnaire (VR Only)		X										
Treatment Usage Questionnaire			X	X	X	X	X	X	X	X	X	X
Events Assessment			X	X	X	X	X	X	X	X	X	
Custom Questions		X									X	
Treatment Expectation	X (Day 4)	X										
Concomitant Procedures Questionnaire	X (Day 4)										X	
Primary Pain Questionnaire											X	
Coping with Weekly Pain Questionnaire	X (Day 7)										X	X

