8.3 ADVERSE EVENTS AND SERIOUS ADVERSE EVENTS

8.3.1 DEFINITION OF ADVERSE EVENTS (AE)

An adverse event (AE) is defined as any untoward medical occurrence associated with the use of an intervention in humans, whether or not considered intervention-related (21 CFR 312.32 (a)). Short-term AEs associated with the study include "cybersickness,"³² a transient form of motion sickness that affects up to one in four people upon entering a VR environment. Cybersickness most commonly presents with a short-term feeling of dizziness that typically subsides quickly. There are no anticipated long-term AEs from participating in this study. A comprehensive list of all potential cybersickness symptoms can be found below:

- Nausea
- Fatigue
- Eyestrain
- Blurred vision
- Difficulty focusing
- Dizziness
- Vertigo (a sensation of spinning dizziness, as though the room or surrounding environment is spinning)
- Headache
- Fullness of the head
- Difficulty concentrating
- Postural instability

In very rare instances, materials used in VR headsets have caused a mild rash which resolves when the VR headset is discontinued. Participants may also experience neck pain if using the device. No AEs are expected with PainTRAINER.

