8.3.3 CLASSIFICATION OF AN ADVERSE EVENT

8.3.3.1 SEVERITY OF EVENT

For adverse events (AEs) the following guidelines will be used to describe severity.

- **Mild** – Events require minimal or no treatment and do not interfere with the participant's daily activities.
- **Moderate** – Events result in a low level of inconvenience or concern with the therapeutic measures. Moderate events may cause some interference with functioning.
- **Severe** – Events interrupt a participant's usual daily activity and may require systemic drug therapy or other treatment. Severe events are usually potentially life-threatening or incapacitating. Of note, the term "severe" does not necessarily equate to "serious".

Research staff will call the patient if an event is noted in event assessment that is sent on a biweekly basis. Nothing more than mild to moderate side effects are expected.

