8.3.3.2 RELATIONSHIP TO STUDY INTERVENTION

All adverse events (AEs) must have their relationship to study intervention assessed by the clinician who examines and evaluates the participant based on temporal relationship and his/her clinical judgment. The degree of certainty about causality will be graded using the categories below. In a clinical trial, the study product must always be suspect.

- **Related** – The AE is known to occur with the study intervention, there is a reasonable possibility that the study intervention caused the AE, or there is a temporal relationship between the study intervention and event. Reasonable possibility means that there is evidence to suggest a causal relationship between the study intervention and the AE.
- **Not Related** – There is not a reasonable possibility that the administration of the study intervention caused the event, there is no temporal relationship between the study intervention and event onset, or an alternate etiology has been established.

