8.3.4 TIME PERIOD AND FREQUENCY FOR EVENT ASSESSMENT AND FOLLOW-UP

The occurrence of an adverse event (AE) or serious adverse event (SAE) may come to the attention of study personnel during review of biweekly event assessments by a study team member as well as on

Day 1. We will employ a general question to allow the patient to provide an event description without bias by presupposing the nature of the event, as follows:

- 1) During the past 14 days, have you experienced anything uncomfortable, distressing or upsetting as a result of using the technology?
 - a. Yes
 - b. No
- 2) If Yes please describe what happened. A research staff member will follow-up with you as soon as possible to learn more.
 - a. [open text]

A designated CRC will review the REDCap dashboard for completed AE assessments on a daily basis throughout the work week. Once they find a completed event assessment form, they will follow-up with a phone call. The following information be obtained from the patient during the call: onset of potential adverse event, event description, when they last used the technology, how long they used the headset, when they stopped using the headset, severity of the potential AE, outcome of the potential AE (see categories, below), time until resolution/stabilization of event, the perceived relationship of the event to the study intervention, whether or not the event was expected (Y/N), whether it was serious.

The outcome can be labeled using one of the following categories:

- Recovered, without treatment
- Recovered, with treatment
- Still Present, no treatment
- Still Present, being treated
- Residual effect(s) present-no treatment
- Residual effect(s) present-being treated

Research staff will record all reportable events with start dates occurring any time after informed consent is obtained until 7 (for non-serious AEs) or 30 days (for SAEs) after the last day of study participation.

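### The scheduled adverse event question reaches only events that participants blame on the technology, so adverse events as section 8.3.1 defines them will be under-ascertained

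*Combined protocol and SAP*

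**What the plan says.** - **Definition (8.3.1).** An adverse event is "any untoward medical occurrence associated with the use of an intervention in humans, whether or not considered intervention-related".
- **Causality (8.3.3.2).** "All adverse events (AEs) must have their relationship to study intervention assessed by the clinician who examines and evaluates the participant". The categories are Related and Not Related, and timing alone is enough for Related.
- **Elicitation (8.3.4).** The aim is stated as: "We will employ a general question to allow the patient to provide an event description without bias by presupposing the nature of the event". The item itself reads: "During the past 14 days, have you experienced anything uncomfortable, distressing or upsetting as a result of using the technology". A Yes opens a free-text box. The follow-up call then collects onset, severity, outcome and "the perceived relationship of the event to the study intervention", along with items that name the headset.
- **Recording window (8.3.4).** It opens at informed consent, before any device is shipped.
- **Frequency.** 8.3.3.1 refers to an "event assessment that is sent on a biweekly basis", and 8.3.4 adds Day 1. In the Schedule of Activities (1.3), the row "Events Assessment" is marked in each of Weeks 1 to 9 and not on Day 1.
- **Analysis.** 9.3 summarises safety by arm in all randomised patients. 9.4.4 makes this descriptive, with no tests.

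**The concern.** The definition excludes causal judgement and the causality rule gives that judgement to a clinician, yet the question asks the participant to make it first. Someone who has a fall, a hospital admission or a spell of dizziness and puts it down to something else can truthfully answer No.

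The trial is fully remote, requires no visits and has no separate data safety monitoring board. The reporting deadline for serious events in 8.3.6 runs from the team's awareness, and the annual review by the Reviewing IRB (10.1.6) sees only what was collected. Both therefore depend largely on this item. The by-arm tables would present participant-attributed events under the name of adverse events.

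**Working it through.** The plan gives no figure for this point, so there is nothing to reproduce. The check is a comparison of sections, followed by two pieces of illustrative arithmetic.

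**1. Which events pass the question?**

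| Event | Within 8.3.1 and the 8.3.4 recording window? | Elicited by the question? |
|---|---|---|
| Attributed to the technology by the participant | Yes | Yes |
| Follows a session, but blamed on something else | Yes; 8.3.3.2 could class it as Related on timing alone | No |
| Unrelated illness or admission during follow-up | Yes; a clinician could grade it Not Related | No |
| Onset between consent and first use | Inside the recording window | No; the technology has not yet been used |

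The second row matters most, because events that the protocol's own rule would call Related can be lost.

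**2. Does another section fill the gap?**
- 8.2 promises follow-up for adverse events generally but words no prompt.
- 8.3.4 could be read as a call after every completed form. However, 8.3.3.1 has staff call when an event is noted, and the second part of the 8.3.4 item promises contact after a Yes.
- The Simulator Sickness Questionnaire is for the VR arm only, on Day 1 of Week 1.
- The EHR extracts in 10.1.8.1 are not assigned to adverse event detection.
- The Concomitant Procedures Questionnaire is marked at baseline and Week 9 and is not described as a safety instrument. The content of the Custom Questions is not given.

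**3. Illustration of size (assumed figures).** Inputs: n = 150 per arm (9.2); true risk p, equal in both arms, assumed 0.25 with range 0.10 to 0.40; attribution shares qV (VR) and qP (PainTRAINER), assumed. One event per affected participant; attributed events are all reported and others are not.

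Reported events per arm = n × p × q. Reported ratio = qV / qP, which does not depend on p. Share missed = 1 − (qV + qP) / 2.

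| qV, qP | Reported at p = 0.25 | Ratio | Share missed |
|---|---|---|---|
| 1, 1 | 37.5 v 37.5 | 1.0 | 0% |
| 0.5, 0.5 | 18.75 v 18.75 | 1.0 | 50% |
| 0.8, 0.5 | 30 v 18.75 | 1.6 | 35% |
| 0.8, 0.2 | 30 v 7.5 | 4.0 | 50% |

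In the last row the apparent risk difference is 0.25 × (0.8 − 0.2) = 15 points. It is 6 points at p = 0.10 and 24 points at p = 0.40. These are examples and not bounds: shares of 0.5 and 0.1 would give a ratio of 5.0. Under-ascertainment arises whenever attribution is below 100%. Distortion between arms arises only if qV and qP differ.

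**4. Overlap of recall windows.** If the item were sent weekly in Weeks 1 to 9 with 14-day recall, an event in any of Weeks 1 to 8 would fall in two windows and a Week 9 event in one. With events spread evenly, that is (8 × 2 + 1) / 9 = 17 / 9 = 1.89 potential reports per event.

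**The case against.** There are several fair points on the plan's side.

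- A reader might infer that unattributed events are never captured. The documents do not support that. 8.3.4 says events may come to staff through the assessments, which is not exclusive wording. 8.2, the support line for both arms, medical record access and recorded reasons for withdrawal are all routes by which a hospital admission could surface. This stands, and the claim is limited to the scheduled question. None of these routes is a specified prompt for both arms.
- A reader might infer that the arms are not comparable on safety. That does not follow either. The schedule row is not restricted by arm, so both arms appear to get the same item, and with equal attribution the ratio is 1.0. Differential attribution is plausible: 4.1 says participants cannot be blinded (6.3 says the opposite), follow-up items name the headset, and 8.3.1 expects no adverse events with PainTRAINER. No figure in the documents shows it.
- A reader might infer that counts are inflated nearly twofold. The figure of 1.9 is a ceiling. It needs weekly sending, a report in both windows and no de-duplication. 8.3.3.1 and 8.3.4 say biweekly, section 10.1.2 refers to 14-day assessments, and the follow-up call records onset, so repeats can be identified.
- The stated aim in 8.3.4 concerns only the nature of the event, and on that the item is open. This stands. The conflict is with 8.3.1 and 8.3.3.2.
- The Reviewing IRB reviews adverse events yearly in place of a monitoring board. That is true, but review cannot restore events that were not elicited.

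**Conclusion.** The scheduled question contradicts the plan's own definition of an adverse event and its rule on who judges causality. Followed as written, it will under-ascertain adverse and serious adverse events that participants do not attribute to the technology, and it cannot reach events between consent and first use. This rests on the wording alone, on attribution being less than complete, and on the instruments whose items are not shown containing no such prompt.

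Bias in the by-arm summaries is possible but not shown; its size depends wholly on assumed attribution shares. No hypothesis test is affected. The timing conflict between section 8.3 and the Schedule of Activities is a separate inconsistency that must be reconciled, and it is not evidence that the item is sent weekly.

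**What to change.** Reword the item for both arms, for example: *Since your last survey, have you had any new or worsening health problem, whether or not you think it is related to the study program?* Let its first use look back to consent, which closes the gap before first use. Ask perceived relation second, and leave causality to the clinician as 8.3.3.2 requires. Reconcile sections 8.3.3.1 and 8.3.4 with the Schedule of Activities, match the recall window to the sending interval, and count each event once by the onset date already collected.

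The direct cost is one changed REDCap item and an amendment. There are three downsides:
- There will be more follow-up calls.
- In a chronic pain population, flares will be reported as adverse events and will overlap with the primary outcome, so they are best tabulated separately.
- The amendment history shows the trial already under way, so ascertainment will differ before and after the change and earlier events cannot be recovered. Summarise the two periods separately.

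If collection is already complete, label the tables as participant-attributed events and do not present them as adverse event incidence.

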8.3.5 ADVERSE EVENT REPORTING

Cedars-Sinai IRB

If a mild or moderate event occurs it does not need to be submitted to the Reportable New Information (RNI). If the event is an unexpected (not usually associated VR side effects) or severe event (requiring treatment), an AE will be submitted to the IRB as soon as possible but within at least 10 working days.

8.3.6 SERIOUS ADVERSE EVENTS REPORTING

SAE will be submitted to the Cedars-Sinai IRB via RNI as soon as possible by study coordinators, but no later than 10 business days from the Principal Investigator's or study team's awareness of the event, incident, information or outcome.

8.3.7 REPORTING EVENTS TO PARTICIPANTS

N/A

8.3.8 EVENTS OF SPECIAL INTEREST

N/A

8.3.9 REPORTING OF PREGNANCY

N/A

8.4 UNANTICIPATED PROBLEMS

8.4.1 DEFINITION OF UNANTICIPATED PROBLEMS (UP)

The Office for Human Research Protections (OHRP) considers unanticipated problems involving risks to participants or others to include, in general, any incident, experience, or outcome that meets all of the following criteria:

- Unexpected in terms of nature, severity, or frequency given (a) the research procedures that are described in the protocol-related documents, such as the Institutional Review Board (IRB)-approved research protocol and informed consent document; and (b) the characteristics of the participant population being studied;
- Related or possibly related to participation in the research (“possibly related” means there is a reasonable possibility that the incident, experience, or outcome may have been caused by the procedures involved in the research); and
- Suggests that the research places participants or others at a greater risk of harm (including physical, psychological, economic, or social harm) than was previously known or recognized.

This definition could include an unanticipated adverse device effect, any serious adverse effect on health or safety or any life-threatening problem or death caused by, or associated with, a device, if that effect, problem, or death was not previously identified in nature, severity, or degree of incidence in the investigational plan or application (including a supplementary plan or application), or any other unanticipated serious problem associated with a device that relates to the rights, safety, or welfare of subjects (21 CFR 812.3(s)).

8.4.2 UNANTICIPATED PROBLEM REPORTING

Study coordinators will report unanticipated problems (UPs) to the Cedars-Sinai IRB as a RNI submission as soon as possible by study coordinators, but no later than 10 business days from the Principal Investigator's or study team's awareness of the event, incident, information or outcome. UPs include SAEs and AEs, which are both unexpected and possibly related to the research as well as SAEs and AEs that meet the definition of a Research-Related Subject Injury (RRSI) – a medical condition that is caused by and/or directly related to the research study (i.e., the condition would not have existed “but for” the subject's participation in the study), and requires diagnosis or treatment.

The UP report will include the following information:

- Protocol identifying information: protocol title and number, PI's name, and the IRB project number;
- A detailed description of the event, incident, experience, or outcome;
- An explanation of the basis for determining that the event, incident, experience, or outcome represents an UP;

- A description of any changes to the protocol or other corrective actions that have been taken or are proposed in response to the UP.

The following are actions that could be taken by the study staff:

1. No action
2. Revise protocol to eliminate apparent immediate hazards to subjects
3. Modification of inclusion or exclusion criteria to mitigate newly identified risks
4. Implementation of additional procedures for monitoring subjects 5 - Suspension of enrollment of new subjects
5. Notify currently enrolled subjects
6. Suspension of research procedures in currently enrolled subjects
7. Modification of consent documents to include a description of newly recognized risks (site and/or study wide)
8. Provision of additional information about newly recognized risks to previously enrolled subjects
9. Other, specify

8.4.3 REPORTING UNANTICIPATED PROBLEMS TO PARTICIPANTS

N/A

9 STATISTICAL CONSIDERATIONS

9.1 STATISTICAL HYPOTHESES

Primary Endpoint(s):

Primary Outcome: Pain interference over time as measured by Daily pain intensity

Hypothesis: EaseVRx will lead to a greater improvement in 7-day average daily pain intensity than PainTRAINER between baseline and week 8.

Comparisons: EaseVRx vs. PainTRAINER .

Secondary Endpoint(s):

Secondary Outcome: Pain interference over time as measured by PROMIS-Pain Interference 8a (T-Scored, Continuous).

Hypothesis: EaseVRx will lead to a greater improvement in pain interference than PainTRAINER between baseline and Week 8.

Comparisons: EaseVRx vs. PainTRAINER .

Secondary Outcome: Pain catastrophizing over time as measured by Pain Catastrophizing scale (PCS) short form.

Hypothesis: EaseVRx will lead to a greater improvement in Pain catastrophizing than PainTRAINER between baseline and Week 8.

Comparisons: EaseVRx vs. PainTRAINER

Secondary Outcome: Anxiety over time as measured by PROMIS anxiety scale.

Hypothesis: EaseVRx will lead to a greater improvement in Coronavirus Anxiety Scale than PainTRAINER between baseline and Week 8.

Comparisons: EaseVRx vs. PainTRAINER

Secondary Outcome: Pain Self-efficacy Questionnaire

Hypothesis: EaseVRx will lead to a greater improvement in Pain Self-Efficacy than PainTRAINER between baseline and Week 8.

Comparisons: EaseVRx vs. PainTRAINER

Secondary Outcome: Comparing the change from study baseline to Week 8 in weekly MME of prescribed medication between baseline and Week 8.

Hypothesis: EaseVRx will have a statistically significant decrease in opioid use in comparison to PainTRAINER between baseline and Week 8.

Comparisons: EaseVRx vs. PainTRAINER

9.2 SAMPLE SIZE DETERMINATION

Sample Size calculations and Power Estimation

Sample Size calculations and Power Estimation

Sample Size Calculation: The primary goal of the study is to test the effectiveness of *PainTRAINER* vs. *EaseVRx*, in reducing pain intensity. The trial will be testing if there is statistical evidence that either *PainTRAINER* or *EaseVRx* is more effective in lowering average weekly pain intensity after 8 weeks from start of intervention. We estimate power to assess the effect of the

Table 1. Minimum detectable odds ratio as a function of the proportion of variability in treatment type that is explained by all other relevant covariates in the model and the baseline probability of positive treatment response.

Baseline probability	R ²			
	0.0	0.1	0.2	0.4
0.2	2.32	2.42	2.55	2.91
0.3	2.17	2.25	2.37	2.69
0.5	2.15	2.25	2.37	2.74

interventions on the treatment response (achievement of a minimally clinically important difference [MCID] of 2.0 on the NRS^{56,57} (y/n)) using logistic regression, accounting for possible confounding factors for the primary outcome described in Aim 1. The dependent variable is the treatment response and the main independent variable of interest is *PainTRAINER* vs. *EaseVRx*. **Table 1** displays the minimum odds ratio that can be detected with 90% power with the two-sided 0.05 level of significance as a function of baseline probability of positive response when a patient is treated with *EaseVRx* and R², the proportion of variability in the predictor of interest that is explained by all relevant baseline covariates in the model using data from 150 patients in the *PainTRAINER* arm and 150 in the *EaseVRx*. For example, data from 300 patients achieve 90% power to detect an odds ratio of 2.25 if the probability of positive response when a patient is treated with *PainTRAINER* is 0.3 and 0.1 of the variability in intervention is explained by all other baseline covariates in the model. These odds ratios vary between 2.15 and 2.91 and are clinically meaningful. Therefore, we have enough power to test statistical significance of predictors in the multivariable logistic regression model. Regarding clinical significance, given an MCID of 2 points on the NRS and a SD of 2 on this scale from our own digital health trials, data from 150 patients in each group

will achieve 90% power to detect a mean pain intensity score difference of 0.75, corresponding to a clinically meaningful effect size of 0.38 SD.

